## **5.0 Enrollment/Randomization**

This is a parallel study where participants will be assigned to either taking the study drug (lanadelumab) or taking the placebo (saline pre-filled syringes.) Patients will be randomly assigned to the treatment order using a permuted-block randomization algorithm. The study drug, lanadelumab, will be shipped from Takeda as pre-filled syringes along with matching placebo, also in prefilled syringes. The Vanderbilt Investigational Drug Services (IDS) will be responsible for the storage, preparation, dispensing, and labeling of the investigational agents. The Vanderbilt IDS will also maintain accurate drug storage and dispensing logs. Subjects will be randomized to receive a placebo or 300 mg of lanadelumab (Takeda Pharmaceutical, Cambridge, MA). Subjects randomized who do

not complete the whole protocol for any reason will be replaced, and their data will be analyzed separately. The half-life of lanadelumab is 14 days, and the time to reach maximum concentration is five days. For this reason, we will monitor blood pressure and the occurrence of DIH for three weeks after the administration of the second dose of the study drug.

[figure not shown]

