The next two consecutive dialysis treatments after each drug administration (days 1 and 3, and days 15 and 17), we will conduct follow-up visits at the dialysis unit to collect information regarding symptoms after discharge from the CRC. During these visits, at the end of every hemodialysis session, we will also inquire, through a standardized questionnaire, about the presence of any symptoms associated with hypotension. This questionnaire will include symptoms such as cramps, dizziness, nausea, and will be scored according to the severity from 0 to 4 (none to severe). We will also collect blood samples at the dialysis unit for pharmacokinetics and special laboratory analysis. During the six-week length of the study, we will monitor the occurrence of DIH episodes and changes in blood pressure in every dialysis session. For this purpose, we will use the dialysis clinic blood pressure monitor logs. We will also conduct two additional visits at the dialysis units (Day 29 and 43) to draw blood, administer the symptomatology questionnaire, and measure blood flow with NIRS. In the final hemodialysis visit (day 43) we will also give the patients an activity monitor that will be collected after five consecutive days of continuous use. During this last visit, we will also administer the QOL questionnaire, obtain the dialysis recovery time, and perform body composition and physical performance tests (except for the six-minute walk test). Details of the study protocol can be found in Figure 5, Tables 1 and 2, and Appendix 1

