## **10.0 Statistical Considerations**

### ***a. Sample size***

The primary outcome will be the change in blood pressure during hemodialysis. For this, we will average blood pressure during hemodialysis of three hemodialysis sessions within the second week of treatment. Secondary endpoints will also be recorded during the second week of treatment and will include the number of hypotensive events, frequency of nursing interventions, average of dialysis recovery times, and average symptoms severity score. Based on our preliminary studies with icatibant and assuming a standard deviation of differences of 13.6 mmHg (pooled SD of the delta), a sample size of 16 in each arm will have 80% power to detect a difference in means of -13.7 mmHg, using a paired t-test with a 0.05 two-sided significance level.

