### ***b. Data analysis plan***

Standard graphing and screening techniques will be used to detect outliers and to ensure data accuracy. Distributions of the continuous outcomes will be assessed for normality. If normality is violated, proper data transformation will be applied, or non-parametric analysis methods will be considered. The primary endpoints are SBP and DBP. The secondary endpoints include heart rate, and the R-R interval (autonomic function), the time to recover after HD, symptoms associated with DIH, and the distance walked during the six-minute walk test.

Mixed effect models will be used to analyze the primary endpoint (blood pressure) with a random subject effect and with the treatment (lanadelumab vs placebo) and the time trend (measurements every 15 minutes) as fixed effects. The focus of this study will be the treatment effect and the time trend of the endpoints; however, mixed effect models also provide the flexibility of controlling for and evaluating covariates. However, we will be careful not to over-fitting the model due to the limited sample size.

Besides the above evaluation of the treatment effect and the time trend through the regression models, the direct treatment effect will also be estimated as within-subject mean difference along with their 95% confidence intervals. For the secondary endpoints, a paired t-test will be performed (lanadelumab vs placebo). If the normality of the data is violated, we will use non-parametric tests.

For binary endpoints (e.g., occurrence of hypotensive events), we will use the McNemar test to compare lanadelumab and placebo.

**Missing Data.** Based on our previous studies, we anticipate a drop-out rate of 10% or less. Subjects who drop out will be replaced. Specific inferences on effects of interest will be made by reporting a point estimate along with a 95% confidence interval and the p-value. Hypotheses will be tested at the level of  $\alpha=0.05$ . We will use SPSS (version 25.0, SPSS, Chicago, IL) and the open-source statistical package R (R Core Team, 2017) for analyses.

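### The DIH event endpoint is a count in one section and yes/no in another, is confined to about three second-week sessions, and leaves the DIH data from all other weeks without an analysis

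*Combined protocol and SAP*

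**What the plan says.** Collection. Section 6.0 (Study protocol) says that over the six weeks "we will monitor the occurrence of DIH episodes and changes in blood pressure in every dialysis session", using the dialysis clinic's blood pressure logs. Section 5.0 cites a 14-day half-life and five days to peak concentration, and for that reason "we will monitor blood pressure and the occurrence of DIH for three weeks after the administration of the second dose".

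Endpoint. Section 10.0a: "Secondary endpoints will also be recorded during the second week of treatment and will include the number of hypotensive events". That is a count, over one week.

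Analysis. Section 10.0b gives its own list of secondary endpoints, which does not include the number of hypotensive events. It assigns secondary endpoints a paired t-test, or a non-parametric test if normality fails. The one line that names a test for hypotensive events begins "For binary endpoints (e.g., occurrence of hypotensive events" and assigns McNemar's test.

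Design. Sections 5.0 and 6.0 describe a parallel-group trial: each patient receives either lanadelumab or placebo.

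**The concern.** DIH is the condition that the trial sets out to treat, so its event endpoint will be read closely even though it is secondary. Three things do not fit together.

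- **Window.** DIH is followed for six weeks, with a stated pharmacological reason to look after the second dose, but the endpoint section uses one week. If the second week means Days 8 to 14, that week contains no session after the second dose (Day 14, a non-dialysis day).
- **Form.** One section has a count and the other a yes/no occurrence. No rule chooses between them, so the choice could be made after the data are seen.
- **Test.** McNemar's test compares paired binary outcomes. Two independent arms provide no pairs.

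At stake is whether a real reduction in DIH would show, and whether the reported DIH result was fixed in advance.

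**Working it through.** **1. Sessions in each window.** Section 4.0 requires thrice-weekly dialysis.
- Six weeks: 6 × 3 = 18 sessions.
- Second week: 3 sessions, or 3/18 = one sixth of those followed.
- Three weeks after dose two (section 5.0): 3 × 3 = 9 sessions.

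**2. What is recorded at those sessions.** Section 4.0 defines DIH as a systolic drop with symptoms. Section 6.0 takes blood pressure from clinic logs at every session. Appendix A marks its combined row for the symptoms questionnaire and blood pressure log only on Days 1, 3, 15, 17, 29 and 43. Four of these follow dose two, and three (Days 15, 17, 29) fall within three weeks of it. None falls in Days 8 to 14. The documents do not say that symptoms are captured at the other sessions.

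**3. The plan's own power figure.** Section 10.0a states that "a sample size of 16 in each arm will have 80% power to detect a difference in means of -13.7 mmHg", "assuming a standard deviation of differences of 13.6 mmHg (pooled SD of the delta" and "using a paired t-test with a 0.05 two-sided significance level". Treated as two independent arms: z = 13.7 / (13.6 × √(2/16)) = 13.7/4.81 = 2.85, and power ≈ Φ(2.85 − 1.96) = 81%; the two-sample t-test gives 78.7%. A paired test with 16 pairs would have 96.4%, so the stated 80% is an independent-arms figure. It concerns blood pressure; no power is stated for DIH.

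**4. Inputs for DIH.**
- From the documents: 16 per arm, two-sided 0.05.
- Proxies for the placebo session rate, both eligibility minimums in section 4.0: 4/12 = 0.33 (inclusion list) and 4/36 = 0.11 (study population text).
- Assumed: rate ratio 0.5, constant over time; beta-distributed patient risk with within-patient correlation ρ from 0.05 to 0.3.

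**5. Hand check at rate 1/3, ρ = 0.1.** Patient risk is Beta(3, 6), so E[p²] = 12/90 = 0.133 and E[p³] = 60/990 = 0.061.
- Any event in 3 sessions, placebo: 1 − (6·7·8)/(9·10·11) = 0.661.
- Any event in 3 sessions, treated: 1 − (1 − 1.5 × 0.333 + 0.75 × 0.133 − 0.125 × 0.061) = 0.408.
- z = 0.253 / √(2 × 0.534 × 0.466/16) = 1.43; power ≈ Φ(−0.53) = 30%.
- Proportion over m sessions: the per-patient variance is 0.0222 + 0.2/m on placebo and 0.0056 + 0.1333/m on treatment; the difference in means is 0.1667.
- m = 3: SE = √((0.0889 + 0.0500)/16) = 0.0932, z = 1.79, power ≈ 43%.
- m = 9: SE = √((0.0444 + 0.0204)/16) = 0.0636, z = 2.62, power ≈ 74%.

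**6. Simulation** (10,000 trials per scenario; two-sample t-test for counts; repeat runs move entries by one or two points). Rate 0.33, halved:

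| ρ | Yes/no, 3 sessions, Fisher | Yes/no, 3 sessions, chi-square | Count, 3 sessions | Count, 9 sessions |
|---|---|---|---|---|
| 0.05 | 21% | 34% | 44% | 81% |
| 0.1 | 19% | 32% | 41% | 72% |
| 0.2 | 15% | 25% | 37% | 58% |
| 0.3 | 12% | 21% | 34% | 47% |

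Relative to the nine-session count, yes/no by chi-square keeps 34/81 = 42% to 21/47 = 45% of the power. The second-week count keeps 44/81 = 54% to 34/47 = 72%.

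**7. Sensitivity.**
- Rate 0.11, halved, ρ = 0.1: yes/no 6% to 15% depending on the test, second-week count 13%, nine sessions 24%. With ρ = 0.3 the gain nearly vanishes.
- Rate 0.33, rate ratio 0.7, ρ = 0.1: 12% (chi-square), 16% (second-week count), 29% (nine sessions).
- Waning effect, rate ratio rising from 0.5 to 0.75 over the nine sessions: 44% at ρ = 0.1, against 41% for a second-week count at full effect; 33% against 37% at ρ = 0.2.

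**The case against.** A reader might infer that the plan reduces DIH to yes/no and so throws away most of the power. The documents do not support that as a general statement. Section 10.0a names a count, the binary line in section 10.0b is only an example, and the rule there for secondary endpoints could send the count to a t-test. On that reading the loss against nine sessions is 28% to 46% of the achievable power. A loss of more than half fits only the yes/no reading at the 33% rate.

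A reader might also infer that the longer window needs no new data. That is not established: DIH is defined with symptoms, and Appendix A schedules the questionnaire at only four sessions after dose two. At the base assumptions with ρ = 0.1, four sessions give 49% power.

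Further objections stand in part. The rate, the effect and the correlation are assumptions, and the eligibility figures are minimums that differ threefold. With a 14-day half-life, Day 43 lies (43 − 14)/14 ≈ 2 half-lives after dose two, so the effect may fade and a longer window may dilute it. The calculations used t-tests on counts, not the models proposed below. The endpoint is secondary, and the blood pressure comparison is unaffected.

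None of this resolves the conflict between sections 10.0a and 10.0b, supplies pairs for McNemar's test, or gives an analysis to the follow-up that section 5.0 justifies.

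**Conclusion.** The concern holds in limited form. The window, form and test of the DIH endpoint are inconsistent across sections 5.0, 6.0, 10.0a and 10.0b; McNemar's test does not fit the design; and no analysis is specified for DIH outside the second week.

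At a 33% placebo session rate and a constant halving, moving to a nine-session count raises power from about 21% to 34% (yes/no, chi-square) or 34% to 44% (second-week count) to about 47% to 81%, for correlations of 0.05 to 0.3. At 11% every option is weak and the gain is small, and a waning effect can remove the advantage over the second-week count. The size is therefore conditional; the inconsistency is not. This is a change that should be made to a secondary endpoint, with moderate confidence in its benefit.

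**What to change.** - Define the second week by study day.
- Replace the McNemar analysis with one prespecified DIH endpoint: sessions with DIH out of sessions dialysed, per patient, over a stated window after the second dose, for example the three weeks in section 5.0.
- Compare the arms as independent groups with a method that allows for within-patient correlation: a logistic mixed model, GEE, or a count model with log(sessions) as offset. Keep it parsimonious, given 32 patients and the plan's own caution about over-fitting.
- Report the second-week count and the window of all sessions after the first dose as supportive analyses.
- Reconcile section 6.0 with Appendix A on whether symptoms are captured at every session. If they are not, analyse the systolic-drop component from the clinic logs at every session, and symptomatic DIH at the questionnaire sessions.
- Reconcile the two eligibility statements in section 4.0 (four episodes in 12 weeks, or in four weeks), since they imply different expected rates.

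The cost is revised analysis wording and modest extra analysis. Recording symptoms at every session would add data collection if it is not already done. The drawback is that the estimate averages over sessions with different drug levels, which is why the window must be fixed in advance and the second-week result kept alongside it.

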## 4.0 Inclusion/Exclusion Criteria

### Study population

Participants will be recruited from Vanderbilt Dialysis Outpatient Clinics. We will enroll patients who are on maintenance hemodialysis for at least six months, with pre-dialysis blood pressure between 110 and 170 mmHg, who are being adequately dialyzed ( $Kt/V > 1.2$ ), and who are between 18 and 85 years old, who have experienced dialysis-induced hypotension (DIH) episodes at least four times in a period of 12 weeks prior to enrollment. We define DIH as the drop of systolic blood pressure (SBP) of more than 30 mmHg with associated symptoms such as nausea, dizziness, cramps, yawning, and abdominal discomfort. We will also look for nursing intervention during the hypotensive episode, but it will not be used as an inclusion criterion. Nursing intervention is defined as a temporary interruption of ultrafiltration, Trendelenburg positioning, or administration of intravenous fluids. We will exclude patients who suffered severe DIH episodes that required the use of vasopressors and the termination of hemodialysis treatment. Patients who have been hospitalized during the last three months or with clinical evidence of inflammatory or infectious disease or with severe anemia (hemoglobin less than 8 g/dl) will be excluded. Institutional review board approval and written informed consent will be

obtained from all study subjects. We expect that 60% of our subjects will be African American and 40% will be women.

*Inclusion criteria*

- Subjects age 18 to 85 years
- On thrice-weekly hemodialysis for at least six months
- Clinically stable, adequately dialyzed (single-pool Kt/V > 1.2), with polysulphone membrane for at least three consecutive months before the study
- Subjects with pre-dialytic systolic blood pressure between 110 and 170 mmHg.
- Subjects with a reduction of systolic blood pressure during hemodialysis equal to or greater than 30 mmHg, with associated symptoms such as nausea, vomiting, muscle cramps, dizziness, or anxiety.
- Hypotensive episodes should occur four times or more in four weeks (12 hemodialysis sessions).

*Exclusion criteria*

- Subjects with intradialytic hypotension that require the use of pharmacological intervention such as midodrine or vasopressin
- Subjects with pre-dialytic systolic blood pressure greater than 170 mmHg or diastolic blood pressure greater than 110 mmHg
- History of myocardial infarction or cerebrovascular event within 3 months

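### The planned comparisons of hypotensive events use paired tests that do not fit two independent arms, and leave out each patient's pre-enrollment DIH count

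*Combined protocol and SAP*

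**What the plan says.** **Design.** Section 5.0: "This is a parallel study where participants will be assigned to either taking the study drug" or placebo. Section 6.0 also describes a parallel-group trial. Each patient receives one treatment only.

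**Eligibility.** Section 4.0 makes a count of earlier episodes a condition of entry, but gives two windows. The inclusion list says: "Hypotensive episodes should occur four times or more in four weeks (12 hemodialysis sessions". The study-population text asks for episodes "at least four times in a period of 12 weeks prior to enrollment". Nursing interventions in those episodes are looked for, but are expressly not an entry criterion.

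**Endpoints.** Section 10.0 a: "Secondary endpoints will also be recorded during the second week of treatment and will include the number of hypotensive events", together with the frequency of nursing interventions. Section 6.0 describes wider data collection: "During the six-week length of the study, we will monitor the occurrence of DIH episodes and changes in blood pressure in every dialysis session".

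**Analysis.** Section 10.0 b: "For the secondary endpoints, a paired t-test will be performed (lanadelumab vs placebo", with a non-parametric test if normality fails. For binary outcomes: "For binary endpoints (e.g., occurrence of hypotensive events), we will use the McNemar test to compare lanadelumab and placebo". Covariates are mentioned only for the blood-pressure mixed model. None is named, and the plan warns there against over-fitting.

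**The concern.** The frequency of DIH before randomisation is the same event in the same patient, so it is the obvious predictor of DIH on treatment. Under the inclusion list it can run from 4 to 12 of 12 sessions. The plan would treat a patient entering at 4 and one entering at 12 alike. With 16 per arm, chance imbalance in this count adds noise to the comparison of the event after which the condition under study is named.

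The two named tests also presuppose that each lanadelumab result is matched to a placebo result. No matching is described. A different test must therefore be chosen, and the plan does not say which, or whether it would use the pre-treatment count.

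**Working it through.** **1. The plan's own figure.** Inputs from Section 10.0 a: difference 13.7 mmHg, SD 13.6 mmHg, two-sided 0.05, 80% power.

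Two independent arms: n = 2 × (1.960 + 0.842)² × (13.6/13.7)² = 2 × 7.85 × 0.985 ≈ 15.5, so 16 per arm. Power at 16 is 81.3% by the normal formula and 78.7% by the two-sample t.

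A paired t-test would need only 10 pairs, and 16 pairs would give 96.4%. The 16 per arm therefore fits independent groups, not the paired test named beside it. No event rate, power or precision is stated for DIH, so there is no DIH figure to reproduce.

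**2. What adjustment can save.** Let r be the within-arm correlation of the qualifying count with the outcome. With 16 per arm and no treatment effect, the variance of the adjusted estimate divided by that of the unadjusted one is about

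(1 − r²) × (1 + 1/28), where 28 = 2 × 16 − 4.

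The second factor is the price of estimating one slope. Break-even is at r² = 1/29, so r ≈ 0.19. Below that, adjustment gains nothing.

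**3. Week-two count.** Everything here is assumed, because the documents give neither a DIH rate in eligible patients nor its spread. Per-session DIH probability is beta-distributed. Entry is at 4 or more of 12 sessions. The outcome covers 3 sessions (thrice-weekly dialysis), with 16 per arm. A two-sample t on counts is compared with analysis of covariance on the qualifying count. Power is for a halved risk.

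| Mean before selection | ICC | r | Variance ratio, no effect | Variance ratio, risk halved | Power, unadjusted → adjusted |
|---|---|---|---|---|---|
| 0.25 | 0.05 | 0.14 | 1.02 | 1.02 | 40.6% → 39.7% |
| 0.25 | 0.10 | 0.24 | 0.99 | 0.98 | 47.6% → 46.4% |
| 0.25 | 0.20 | 0.37 | 0.88 | 0.93 | 56.1% → 57.9% |
| 0.25 | 0.30 | 0.47 | 0.81 | 0.88 | 62.0% → 67.8% |
| 0.40 | 0.05 | 0.17 | 1.02 | 1.01 | 57.9% → 57.4% |
| 0.40 | 0.10 | 0.28 | 0.95 | 0.98 | 60.9% → 61.3% |
| 0.40 | 0.20 | 0.42 | 0.87 | 0.92 | 66.6% → 70.4% |
| 0.40 | 0.30 | 0.51 | 0.77 | 0.86 | 71.8% → 77.9% |

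Check of step 2: r = 0.47 gives (1 − 0.22) × 1.036 = 0.81, as simulated.

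A second set of assumptions (mean 0.3–0.5, between-patient SD 0.15–0.25) gives r = 0.26–0.50 and a variance ratio of about 0.87–0.99 with risk halved. Power rises by about 0 points at SD 0.15, 1.5–3.6 at SD 0.20 and 5–6 at SD 0.25.

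**4. Any event in week two.** The qualifying count correlates 0.11–0.29 with this outcome. 0.11² ≈ 0.01 and 0.29² ≈ 0.08, so about 1–9% of variance is saved before the price of the slope.

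The form of the endpoint matters more. For a halved risk, Fisher's test on any week-two event has about 21–25% power, against 41–72% for the unadjusted count. Over 18 sessions about 99% of untreated patients have an event, so the binary form then carries almost no information.

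**5. Count over six weeks (about 18 sessions).** With risk halved, the variance ratio is 0.59–0.96 over the ICC grid above. At SD 0.15–0.25 the saving is about 15–42% of variance. A repeat run with 20,000 trials per setting gave 12–38%, so the ends are good to a few points only. Power on the ICC grid is already 95% or so without adjustment and rises by 0 to 3.4 points (largest: 96.0% → 99.4%). The benefit there is mainly a narrower confidence interval.

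**The case against.** The strongest reply is that, for the endpoint as pre-specified, little is lost. Section 10.0 a fixes the window at week two, about three sessions, and the entry rule narrows the range of the qualifying count. Under low between-patient variation, adjustment gains nothing. The larger savings need a six-week analysis window. Section 6.0 collects those data but does not make them the endpoint. All of this stands, and it limits the size of the point.

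A second reply is that the paired tests are the real fault and the covariate is an add-on. That is fair as to order of importance. But replacing them with Fisher's test or a two-sample t-test would still discard the pre-treatment count, so the choice of replacement is the moment to decide on it. One pre-specified covariate is compatible with the plan's caution about over-fitting.

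Three stronger readings are tempting, and the documents do not support them:

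- *The count is recorded and then ignored.* The documents imply that episodes are counted. They do not say that the number, rather than criterion met or not met, becomes study data. For nursing interventions the inference is weaker still, because they are not an eligibility item.
- *Adjustment would lift power from 80% to as much as 90%.* This follows from a large-sample shortcut, Φ(2.80/√(1 − r²) − 1.96), at r = 0.50. But the plan's 80% belongs to blood pressure. The shortcut also ignores the cost of the slope and assumes the same correlation in both arms, whereas halving the risk moves the variance ratio closer to 1 in most settings.
- *The qualifying window is 12 sessions.* That is one of two conflicting windows. Twelve weeks would be about 36 sessions, and the figures above do not cover that case.

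**Conclusion.** The point holds in a limited form. Every randomised patient must have had DIH episodes counted before entry. Neither planned comparison of hypotensive events uses that count, and neither suits independent arms.

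The gain from using it depends wholly on assumed DIH rates and between-patient variation. For the pre-specified week-two count it is nil to about 6 points of power, for the binary week-two outcome it is slight, and only for a six-week count is it substantial (roughly 15–40% of variance).

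A reader might infer that the trial is underpowered for DIH because of this omission. The documents do not support that: they make no power claim for DIH, and none of their stated figures is shown to be wrong by this point. The endpoints concerned are secondary; blood pressure is not affected. The grade is consider.

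**What to change.** In Section 10.0 b, replace the paired t-test and McNemar test for hypotensive events with a between-arm regression of DIH sessions out of sessions attended. It could be quasi-binomial, or negative binomial with sessions as offset, with treatment and the pre-enrollment DIH rate as the one pre-specified covariate. State the analysis window. If the six monitored weeks are wanted as well as week two, say so in advance.

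Enter the actual qualifying count and the number of sessions reviewed on the case report form. Reconcile the two look-back windows in Section 4.0, so that the covariate means the same thing for every patient. The list and the text also word the pressure-drop threshold differently (30 mmHg or more against more than 30 mmHg), and one definition should serve both look-back and follow-up.

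Treat nursing interventions in the same way only if their pre-enrollment count is captured for every patient.

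The cost is SAP wording, a data field that screening should already yield for DIH, and one degree of freedom. If patients barely differ in DIH frequency, nothing is gained and about 1–2% of variance may be lost. Capturing nursing interventions would be extra work.
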